PROTOCOL TITLE: The Effects of Transcranial Direct Current Stimulation on the Neuronal Mechanisms of Cognitive Control in Schizophrenia

1) Protocol Title

Title: The Effects of Transcranial Direct Current Stimulation on the Neuronal Mechanisms of Cognitive Control in Schizophrenia
Protocol Version Date: 9/23/2019

2) Objectives

The purpose of this study is to better understand the neural correlates of cognitive control (CC) deficits in schizophrenia and determine how these mechanisms can be modulated by transcranial direct current stimulation (tDCS). CC is a critical neurocognitive process that is required for flexible, directed thought and action based on goals and intentions. Identifying and developing paradigms to improve CC is therefore a mental health priority. Current theories of CC postulate that recruitment of the dorsolateral prefrontal cortex (DLPFC) is essential for this process by maintaining high-level information that it can then use to orchestrate patterns of activation in other brain networks to support optimal performance. tDCS is a safe, noninvasive method of modulating regional brain excitability via brief (15-20 m) application of a weak (1-2 mA) current. The goal of the proposed experiments is to combine tDCS with functional magnetic resonance imaging (fMRI) or electroencephalography (EEG) to test the hypotheses that 1) acute tDCS over the DLPFC can improve performance during a CC task (the dot pattern expectancy (DPX) variant of the AX-CPT) in schizophrenia, and 2) acute tDCS over the DLPFC can increase recruitment of the DLPFC during the DPX. Sham stimulation over the DLPFC and acute stimulation over the somatomotor cortex (SMC) will also be performed as control conditions. Effects of tDCS on brain functional connectivity (during CC as well as during the resting state) will also be examined, as well as effects on an episodic memory task. EEG recordings will be incorporated into this study in order to better understand the physiological mechanisms associated with cognitive function, as well as with non-invasive stimulation. The current study will be the first to use fMRI to examine the effects of tDCS on the neuronal mechanisms of CC in schizophrenia, and has potentially important implications for therapeutic development for this treatment refractory yet disabling aspect of the illness.

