This study will enroll approximately 250 patients with schizophrenia and 50 demographically (age/gender) matched control subjects. Depending on the success of our methods, the overall study is projected to last up to 5 years. An individual subject's participation will generally consist of six visits (a screening/questionnaire/interview visit, three stimulation visits with fMRI or EEG and two non-stimulation visits with fMRI or EEG).

In addition to a clinical/screening visit, this study will incorporate a crossover design consisting of 5-10 sessions separated by at least 24-48 hours.

For these sessions, the tDCS protocol (sham with task, DLPFC with task, sham without task, DLPFC without task, or SMC stimulation) may be followed by fMRI or EEG. Up to 4 tDCS sessions (2 sham, 2 stim) may be conducted without fMRI or EEG afterwards. The order of sessions (sham with task, DLPFC with task, sham without task, DLPFC without task, or SMC stimulation) will be randomized and counterbalanced for each group (patients and controls).

The estimated study completion date is March 1, 2022, with all subjects expected to be enrolled by March 1, 2021, and all primary analyses complete by March 1, 2022.

6) Study Endpoints

Participation for each subject is considered complete following participation in all of the tDCS conditions and sessions (sham with task, DLPFC with task, sham without task, DLPFC without task, and SMC stimulation) for an experiment. Although we do not anticipate any safety concerns, studies may be terminated prior to completion in the case of any skin irritations, lesions or other adverse reactions to stimulation. Subjects may also choose to withdraw at any point during the study.

7) Procedures Involved

Recruitment Methods. Healthy young adult participants will be recruited by ads and word of mouth from the UC Davis community; ads will be placed in the Department of Psychology, Center for Neuroscience, or UCDMC as well as around the community (grocery stores, churches, community centers, coffee shops, etc). These flyers are included in the IRB application. Ads will also be placed on our lab web page. Additional subjects will be recruited through the Sona system paid

PROTOCOL TITLE: The Effects of Transcranial Direct Current Stimulation on the Neuronal Mechanisms of Cognitive Control in Schizophrenia

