No identifiers, used for recruitment purposes, will be disclosed to a third party except as required by law or for authorized oversight of the research project.

General Procedure . Overall, during testing sessions subjects will first undergo the tDCS protocol assigned to that session (sham with task, DLPFC with task, sham without task, DLPFC without task, and SMC stimulation) immediately followed by MRI scanning, or EEG recording. MRI scanning will consist of (in order): prescanning procedures (e.g. high order shim, anatomical (T1) scan), a CC task (the Dot-Probe Expectancy (DPX) task), an episodic memory task (The Relational and Item-Specific Encoding (RISE) task) and a 10 minute resting state scan.

Prior to the start of each experiment, the participant will be properly consented and fill out a demographic form. This demographic form may be a paper version or a Google form. We will record subject number, gender, age, racial background, and ethnic background on the form. Completion of the form is entirely optional and subjects can choose not to answer any of the questions on the form. The subject number is a code that carries no personal identifiable information. Only researchers on the Research Personnel list have access to the answers stored on the Google Drive. All demographic forms will be stored in locked file cabinets in lab space. Only researchers on the Research Personnel list have access to the file cabinets.

Subjects without previously confirmed diagnoses of schizophrenia or schizoaffective disorder will then undergo the Structured Clinical Interview for DSM-V (SCID), and a complete psychiatric history will be taken.

Subjects will then undergo diagnostic (clinical) interviews if no current clinical ratings/information are available (ratings < 1 month old are considered current). These rating scales will include the Brief Psychiatric Rating Scale (24 item), the Scale of the Assessment of Positive Symptoms, the Scale for the Assessment of Negative Symptoms, and may also include the following (see attached packets for actual questionnaires):

The Global Functioning Scales

The Global Functioning Scale: Social (GFS: Social; Auther et al., 2006) and Global Functioning Scale: Role (GFS: Role; Niendam et al., 2006a) provide ratings of functioning in social and role domains, respectively, on two separate 10-point Likert scales, which are scored independently of symptom severity.

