“Stimulation Only” or “Stimulation and EEG” electrodes may be used (see electrode chart above). Note, for ease of these experiments, the “Stimulation Only” electrodes will be used in most cases. For these electrodes, sponge electrodes will be moistened (with saline), prior to placement on the subject’s scalp. Alternatively, “Stimulation and EEG” electrodes (PISTIM) will be applied using conductive electrode gel. See chart above for electrode sizes and specification. Up to 8 electrodes may be used at any given time (in addition to external/reference electrodes. See above). Only scalp electrode sites designated on the Starstim cap will be used. The cap only uses standard electrode sites from the 10-20 system.

tDCS stimulation (~25 minutes). During this phase, participants will first receive a few minutes of training on the DPX task and complete a brief practice session. Subjects will also be familiarized with the working memory task (see below). After practice, stimulation (or sham stimulation) will begin.

Following the practice session, subjects will undergo sham with task, DLPFC with task, sham without task, DLPFC without task, or SMC active stimulation. The order of the conditions will be fully counterbalanced across subjects. This experiment involves five tDCS visits, and may include tDCS at any of the designated scalp electrode sites in the Starstim cap. Each stimulation visit will be separated by at least 24-48 hours.

Subjects will receive up to 20 minutes of tDCS stimulation or sham, in addition to a few seconds of ramp up and ramp down time at the beginning and end of each session, using the Starstim device. All subjects will receive up to 2.0 mA for the first 30-60 s of stimulation. Current strength will be ramped down, and then reduced to 0.0-0.1 mA in subjects receiving sham stimulation for the remainder of the session. The active stimulation subjects will continue to receive up to 2.0 mA stimulation. Many participants can feel the onset of the stimulation (which leads to a brief tingling or itching sensation), but people cannot generally feel the continued stimulation beyond one minute. By beginning both the active and sham stimulation conditions with a period of stimulation, we can ensure that participants will not

PROTOCOL TITLE: The Effects of Transcranial Direct Current Stimulation on the Neuronal Mechanisms of Cognitive Control in Schizophrenia

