In the three-back task, subjects will be asked to remember the location of an object presented three objects previously on a computer screen. To register a match, a key on a keypad, keyboard, or mouse will be pressed. No response is required for non-targets.

Wash up: The stimulating electrodes will be removed, cleaned, and disinfected according to the manufacturers instructions. As the electrodes are removed, the experimenter will inspect the skin at and near the electrode sites for redness, irritation, or damage and note if present.

For sessions that include fMRI scans, scanning will begin immediately following wash-up and will last up to 1 hour (Stimulation will only last for 20 minutes). See above for specific imaging procedures.

Mood Assessment (30-90 minutes):

PROTOCOL TITLE: The Effects of Transcranial Direct Current Stimulation on the Neuronal Mechanisms of Cognitive Control in Schizophrenia

After imaging is complete, participants will undergo a relaxation period (~30 minutes) during which the electrodes will be removed and the participants will relax (by sitting quietly or watching a video). Subjects will then take the mood and mental state questionnaire again to make sure that they have no lingering effects of the stimulation. In the unlikely case that a subject still has any lingering effects, the subject will relax for an additional 15 minutes, and then repeat the mood/mental state assessment. This will be repeated until the participant returns to baseline. There are no known reports of lingering effects of tDCS after 90 minutes, so we anticipate that the relaxation period will be complete within 90 minutes in all participants. We will also perform a 48-hour follow-up call or email to ensure that subjects have not experienced any additional adverse effects.

Compensation. Subjects will be compensated \$25 for completing the questionnaires and clinical interview, \$25 for each tDCS session that does not include fMRI or EEG afterwards, \$75 for each tDCS session that is followed by fMRI or EEG, and given a \$50 bonus for completing all sessions of a given modality (EEG or fMRI).

8) Data and/or Specimen Management and Confidentiality

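### Could the allowance for sessions without fMRI or EEG leave a completed participant with no sham scan?

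*Protocol*

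**What the plan says.** Section 5 (Study Timelines) makes three statements about sessions. After screening, a participant generally has "three stimulation visits with fMRI or EEG and two non-stimulation visits with fMRI or EEG". The study is "a crossover design consisting of 5-10 sessions separated by at least 24-48 hours". And of those sessions, "Up to 4 tDCS sessions (2 sham, 2 stim) may be conducted without fMRI or EEG afterwards".

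Section 6 (Study Endpoints) sets completion: "Participation for each subject is considered complete following participation in all of the tDCS conditions and sessions", with five conditions named. Two are sham (with and without task) and three are active (DLPFC with task, DLPFC without task, SMC). No scan is mentioned.

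Section 7 (Procedures Involved) touches the point in several places:

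- The General Procedure says that the assigned tDCS is "immediately followed by MRI scanning, or EEG recording".
- A later paragraph says that fMRI or EEG may follow only some of the stimulation sessions.
- The tDCS stimulation paragraph says "This experiment involves five tDCS visits".
- The Compensation paragraph sets a $25 rate "for each tDCS session that does not include fMRI or EEG afterwards", a $75 rate for sessions with imaging, and a $50 bonus for finishing every session of one modality.

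The second hypothesis in section 2 (Objectives) is that "acute tDCS over the DLPFC can increase recruitment of the DLPFC during the DPX", with sham stimulation as a control condition.

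**The concern.** The allowance covers two sham sessions, and the five-condition design has only two sham sessions. If the four unimaged sessions may be taken from the five condition sessions, a participant can lose both sham scans and still be complete under section 6, which asks for sessions and not for scans.

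The imaging hypothesis compares DLPFC stimulation with sham, and the strength of a crossover is that this comparison is made within a person. A participant without a sham scan gives no such comparison. The No-Task Sessions paragraph in section 7 also wants sham and stimulation compared with and without a concurrent task. For imaging, that needs both sham and both DLPFC sessions scanned. No analysis can recover a scan that was never made, so the question belongs to the protocol.

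The counts also look inconsistent: five imaged visits, 5 to 10 sessions, up to four without imaging, and five tDCS visits do not obviously describe one schedule.

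**Working it through.** **Inputs.** All come from sections 5 to 7: one screening visit; 3 + 2 imaged visits; 5 to 10 sessions; five conditions (2 sham, 3 active); at most 4 unimaged sessions (2 sham, 2 active); five tDCS visits.

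**1. The plan's own count.** Visits: 1 + 3 + 2 = 6, as stated. Imaged visits: 3 + 2 = 5. The split of three and two matches three active and two sham conditions if non-stimulation means sham.

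**2. Reading A: the four are among the five condition sessions.** Full use leaves 5 - 4 = 1 imaged session. Both sham sessions and two of the three active sessions are unimaged, so the remaining scan is SMC, DLPFC with task, or DLPFC without task. There is no sham scan.

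To see how far partial use matters, treat the two figures of 2 as caps (an assumption; the text does not say so).

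- Sham sessions left unimaged: 1 + 2 + 1 = 4 ways.
- Active sessions left unimaged, at most two of three: 1 + 3 + 3 = 7 ways.
- Permitted patterns: 4 x 7 = 28.
- No sham scan: 1 x 7 = 7.
- Both task-matched DLPFC/sham pairs imaged: only SMC may be missing, so 2.
- Exactly one pair imaged: for each pair, the other pair is broken in 3 ways and SMC is imaged or not, so 2 x 3 x 2 = 12.
- No pair imaged: 28 - 2 - 12 = 14.

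These count what Reading A would permit. They are not probabilities.

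**3. Reading B: the four are additional to the five imaged visits.** Sessions: 5 + 4 = 9. The fewest imaged sessions under full use is the session count minus 4:

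| Sessions | 5 | 6 | 7 | 8 | 9 | 10 |
|---|---|---|---|---|---|---|
| Fewest imaged | 1 | 2 | 3 | 4 | 5 | 6 |

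Five imaged visits and full use of the allowance fit together at 9 or 10 sessions, both within the stated range. No scan is lost.

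**4. Which reading does the text favor?** Reading A with full use gives one imaged visit where section 5 lists five. Reading B keeps the list and gives the range of 5 to 10 a purpose: five sessions without the extra block, nine with all of it. The four unimaged sessions are then among the 5 to 10 sessions but not among the five imaged ones, which agrees with both sentences. Two sham and two stimulation sessions also match sham and DLPFC, each with and without task, which looks like a planned block and not like scans dropped at will. The separate pay rate, and a bonus tied to all sessions of a modality, point the same way. None of this is proof, but it all leans to Reading B.

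**5. What does not fit Reading B.** Section 7 states five tDCS visits, against nine under full use. That sentence speaks of one experiment, section 3 (Background) announces a series of them, and section 6 defines completion per experiment, so five may be a per-experiment count. Nine sessions plus screening is 1 + 9 = 10 visits, against a stated six, but the six are given only as the general case. A total of 10 + 4 = 14 arises only if the 10 is taken as five sessions in each modality with the four added on top, and the ceiling of 10 rules that out.

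**The case for a change.** The best case for a change is that no reading fits every sentence. Reading A breaks the list of five imaged visits, and Reading B breaks the count of five tDCS visits. The protocol sets no minimum number of scans, does not say which sessions must be imaged, and counts a participant as complete without any. Unimaged sessions are clearly expected, since they have a price. One clarifying sentence would cost little and, under Reading B, would add no scans.

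The textual part of this stands: section 5 does not say whether the four are within or beyond the five, and the count in section 7 is not aligned with it. The consequence is weaker than it looks.

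- The loss is permitted under one reading only, the allowance is optional, and its expected use is not given.
- In two of the three full-use patterns of Reading A a DLPFC scan remains. It can still be compared with other participants' sham scans or enter a mixed model. Only the within-person contrast is lost.
- Section 6 says when participation ends. It does not define who enters the imaging analysis; that rule is commonly left to the SAP, which is not at hand.
- The General Procedure's line that imaging follows at once is a general description, and the same section says openly that imaging follows only some sessions.

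A loss of precision can be written down: if a fraction f of participants has no imaged pair, the standard error of the paired contrast grows by 1/sqrt(1 - f), for example 1/sqrt(0.5) = 1.41 at f = 0.5. But the protocol gives no basis for any f. Applying the factor to all 250 patients or 50 controls would also treat them as one imaging sample, although sessions use fMRI or EEG. The formula shows what missing scans do in any trial and does not measure a defect of this one.

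**Conclusion.** The wording is incomplete, but the design is not at fault, and no change to the plan is called for. The protocol's own visit list gives five imaged visits, two of them non-stimulation. Investigators who keep to it retain both sham scans and both DLPFC scans, and up to four unimaged sessions on top make nine, within the stated range. Writing this down would mainly record what they would do anyway.

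The size is correspondingly small. Under the reading that fits section 5, no scan is lost. Under the other, full use leaves one imaged session and removes that participant's within-person DLPFC-versus-sham imaging contrast, though in two of three patterns a DLPFC scan remains usable between persons.

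The conclusion assumes that non-stimulation means sham, that the visit list governs which sessions are imaged, and that the five tDCS visits in section 7 are a per-experiment count or a loose one. If the investigators did intend unimaged sessions to replace the sham scans, the concern would be real; nothing in the document says that they did.

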We will use tDCS to stimulate specifically the DLPFC or SMC, and we will concurrently measure the effects of the stimulation on CC by means of behavioral measurements of accuracy and reaction time. These may be combined with fMRI or EEG after some of the stimulation sessions to measure brain response during a CC task as well as the resting state. The fMRI and EEG measurements are noninvasive. The CC paradigm we will use is described below.

Prior to the start of an experiment, the experimenter will explain all of the experimental procedures to the participants, and the participants will read and sign consent forms if they agree to participate. To familiarize subjects with test procedures, prior to tDCS stimulation subjects will complete a short practice session on the DPX task on a computer screen outside of the MRI scanner. Subjects unfamiliar with MRI scanning procedures may also participate in a mock scanning session (mock scanner that visually resembles the actual MRI scanner) prior to tDCS.

For fMRI sessions, subjects will perform the DPX and RISE tasks while lying supine in the MRI scanner. For EEG sessions, subjects will be seated in a

PROTOCOL TITLE: The Effects of Transcranial Direct Current Stimulation on the Neuronal Mechanisms of Cognitive Control in Schizophrenia

comfortable chair in front of a computer screen. Participants will be presented with visual (e.g., a picture of an object) stimuli. Participants will be asked to make responses to the series of visual stimuli using a numbered pad or keyboard. To constrain learning strategies, participants may be asked to make a simple perceptual or semantic judgment about each stimulus. See below for further details regarding the DPX and RISE tasks. At the end of the session, participants will be debriefed and they will remain in the laboratory in a relaxed state until mood and mental state return to baseline. More details about the experimental design are highlighted below.

Following the completion of each experiment, participants will be fully debriefed on the goals and hypotheses of the experiment and be given the opportunity to provide feedback regarding their experiences and strategies that they used in the study. Below is a table summarizing the possible stimulation parameters that may be used in the proposed experiments:

Stimulation sites	Number of stimulation electrodes	Stimulation electrodes	Current parameters

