tDCS. We will use the Starstim device (Neuroelectrics) prior to having subjects complete the DPX, RISE, and resting state fMRI scans. Electrodes (metallic disks with wires attached) are used to stimulate the brain at the scalp. During stimulation, the participant sits comfortably in a chair in a sound-attenuating, electrically shielded room (dimensions: 10'x 8' with a ceiling height of 8') while performing a working memory task (n-back, see below) to engage the DLPFC. Electrodes and caps are sterilized between uses and dried completely prior to next use. Application materials are discarded after every use and new materials are utilized for each participant.

StarStim system. The electrodes used with the StarStim device will be or "Stimulation Only" or "Stimulation and EEG" electrodes listed above. The

PROTOCOL TITLE: The Effects of Transcranial Direct Current Stimulation on the Neuronal Mechanisms of Cognitive Control in Schizophrenia

electrodes are worn in an elastic cap that is commercially available from Neuroelectrics. The scalp is cleansed (alcohol may be used) and prepared using a non-toxic electrically conductive gel (except in the case of dry electrodes- see below) that is placed between the electrode surface and the scalp. Standard StarStim equipment protects the participant from any hazard of electrical shock using isolated grounding procedures.

tDCS/Sham Stimulation Session Procedure

Mood and Mental State Assessment (5 minutes). A 1-page questionnaire (see attached) will be administered. This brief mood and mental state questionnaire will serve as a baseline for the subject's mood and mental state.

tDCS preparation (~10 minutes). Prior to electrode placement, the skin at the electrode sites will be inspected to ensure that it is free of abrasions or irritation. The area will then be gently cleaned with rubbing alcohol, but not abraded.

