know if they are receiving active or sham stimulation. The sham conditions serve as an important control, which is similar in procedure and results in similar initial sensations, but does not provide a significant level of stimulation. The SMC stimulation condition is another important, "active" control that controls for the effect of stimulation at a location other than the DLPFC area of interest for which tDCS is hypothesized to have effects on CC.

A sensation questionnaire will be administered at 3 separate time points during stimulation, starting at approximately 5 minutes after the beginning of stimulation, and then approximately every 10 minutes during stimulation. In this assessment, subjects will be asked to report the level of sensation arising from the stimulation on a 10 point scale, with 1 meaning no sensation and 10 meaning mild pain. Stimulation will be terminated immediately if the reported sensation level is 7 or higher at any assessment. Participants—who will be in constant communication with an experimenter—will also be instructed to inform the experimenter if pain is experienced at any other time, which will lead to immediate termination of stimulation. Additionally, the experimenter will monitor the electrodes to ensure that they do not dry out or otherwise cause discomfort.

No-Task Sessions: While subjects are undergoing sham without task or direct current stimulation without task they will rest quietly while seated at a computer desk. The experimenter will be available to chat with the participants and administer the sensation questionnaires as described above. The purpose of the No-Task sessions is to be able to compare the effects of sham/stimulation without task to sham/stimulation with a concurrent task, as previous work has suggested that there may be a benefit to completing a concurrent task during tDCS (see below).

Concurrent Visuospatial N -Back Working Memory Task: While subjects are undergoing sham or direct current stimulation they will concurrently perform a simple "n-back" (three-back) working memory task. This is because tDCS effects on tasks that engage the prefrontal cortex (e.g. the DPX) are enhanced if the stimulation occurs at the same time as either the same task or another task that also engages the prefrontal cortex (i.e. "state-dependent" effects) (Tremblay et al., 2014).

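### Does the protocol give two different timings, during and after stimulation, for the cognitive control outcome?

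*Protocol*

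**What the plan says.** Section 2 (Objectives) makes performance on the DPX the subject of hypothesis 1. In Section 7, an introductory paragraph states that "we will concurrently measure the effects of the stimulation on CC by means of behavioral measurements of accuracy and reaction time". It adds that fMRI or EEG may follow some of the sessions, and that "The CC paradigm we will use is described below". The DPX Task subsection then scores CC by the difference between AY and BX trials.

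The operational parts of Section 7 describe a different sequence:

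- General Procedure: "subjects will first undergo the tDCS protocol assigned to that session", and this is "immediately followed by MRI scanning, or EEG recording". The DPX is listed as part of the scan.
- tDCS: the device is used "prior to having subjects complete the DPX, RISE, and resting state fMRI scans". During stimulation the subject is "performing a working memory task (n-back, see below) to engage the DLPFC".
- No-Task Sessions: "they will rest quietly while seated at a computer desk". Their purpose is to "compare the effects of sham/stimulation without task to sham/stimulation with a concurrent task".

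Section 5 (Study Timelines) permits up to four tDCS sessions, two sham and two active, with no fMRI or EEG afterwards. Section 7 does not say whether the DPX is given in them.

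**The concern.** When a task is given relative to stimulation is part of the definition of the outcome. A DPX taken under current and a DPX taken afterwards measure different things. The protocol itself argues that doing a task during stimulation strengthens the effect, so a DPX given at that point would be part of the intervention as well as its measurement. If some sessions tested CC during stimulation and others after it, the DLPFC-versus-sham comparison for hypothesis 1 would mix two outcomes. A DPX during the no-task sessions would also remove the contrast those sessions exist to provide.

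The second worry is missing data. The introductory sentence treats behavioural measurement as the base and imaging as an addition after some sessions, so a reader may expect a CC score from every session. For sessions without fMRI or EEG, the concurrent measurement is the only one written, and the procedures leave no room for it.

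**Working it through.** The protocol gives no figure to reproduce, because the question is one of sequence. The check is to set out what the text places before, during and after stimulation for each type of session.

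| Session type | Before | During | After |
|---|---|---|---|
| With fMRI | DPX training and practice | n-back, or rest in no-task sessions | DPX, RISE and resting scan in the scanner |
| With EEG | DPX training and practice | n-back, or rest in no-task sessions | Recording with a cognitive task and/or rest; the DPX is implied by the pointer to the task descriptions |
| Without fMRI or EEG (optional, up to 4) | DPX training and practice | n-back, or rest in no-task sessions | No CC test written |

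**1. Is a DPX during stimulation described anywhere?** There are five conditions: sham with task, DLPFC with task, sham without task, DLPFC without task, and SMC. In the two no-task conditions the subject rests. In the other three, the only task written for the stimulation period is the n-back. So a DPX during stimulation is directed in 0 of 5 conditions and excluded by definition in 2 of 5.

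**2. Could the sentence mean the n-back?** No. The protocol calls the n-back a working memory task used to engage the DLPFC, and it is absent from the no-task sessions. CC is defined through the DPX.

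**3. Which reading fits the rest of the text?** The same passage of Section 7 goes on to put the DPX in the scanner for fMRI sessions. The sentence therefore reads most naturally as saying that behavioural measures are collected alongside the stimulation study. On that reading it agrees with the General Procedure and with the tDCS, No-Task Sessions and Wash up text.

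**4. Do the sessions without imaging take data from hypothesis 1?** Section 5 describes the usual participation as six visits: 1 screening + 3 stimulation with fMRI or EEG + 2 non-stimulation with fMRI or EEG. That leaves 3 + 2 = 5 imaged visits, which matches three active and two sham conditions. Section 5 also allows 5 to 10 sessions, which leaves room for more than five. The Compensation paragraph pays separately for sessions with and without fMRI or EEG. The text therefore leans towards the optional sessions being additional. On that reading each condition keeps its imaged visit, and extra sessions without a DPX subtract nothing from the comparison.

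**The case for a change.** The strongest case for a change is that timing is a matter of session procedure. No statistical analysis plan can recover a DPX that was not given, or was given at the wrong moment. The n-back text also says prefrontal effects are enhanced by doing either the same task or another prefrontal task during stimulation. A literal reader could therefore think a DPX under current was intended.

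The first part is right in principle. It would carry weight if any procedure directed a DPX during stimulation, or if two operational sections disagreed. Neither is so. To act on the literal reading, staff would have to override the tDCS text, the n-back text and the instruction to rest in no-task sessions, on the strength of one word in a summary.

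What stands is that the adverb is wrong as written, and that the protocol does not say whether the optional sessions have a CC outcome. Stating that they have none would be enough to close the second point, so it is an unstated choice. Better wording would record what the procedures already do, and it would alter no comparison.

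**Conclusion.** No change to the plan follows. The mismatch is one adverb in an introductory sentence, set against consistent operational text that gives one order: practice, stimulation with n-back or rest, then testing. A DPX during stimulation is directed in none of the five conditions, so the feared mixing of timings does not arise from following the protocol. The silence about what is tested after stimulation in sessions without fMRI or EEG concerns up to four optional sessions per subject. Analysts can sensibly draw the CC outcome from the sessions in which a DPX was given after stimulation.

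This rests on two assumptions. The first is that staff follow the detailed procedures where the summary sentence differs. The second is that the optional sessions are additional to the five imaged visits, which the visit schedule in Section 5 favours but does not state outright. If they replaced condition visits, some DLPFC or sham visits could lack a written DPX, and the silence would matter more.
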